Funder(s)	Yorkshire Cancer Research
	[name]
	Harrogate
	[name]
Key Protocol Contributors	[name]
	[name]
	[name]
Committees	Contact details for TSC and DMC to be included
	here

STUDY SUMMARY

Study Title	E-cigarettes for Smoking Cessation And reduction in
	People with mEntal illness (ESCAPE trial)
Internal ref. no. (or short title)	ESCAPE trial
Study Design	Phase I is a randomized controlled feasibility trial with an embedded process evaluation, comparing the intervention (e-cigarette starter kit as an adjunct to usual care) and control groups (usual care) at 1-month follow-up. Phase II, full RCT - similar approach to the feasibility trial with a follow-up point at 6 months.
Study Participants	Participants will include adults (> 18 years) currently receiving treatment for a mental illness under the care of secondary care psychiatric community teams or community mental health teams (CHMTs) at three Northern Mental Health Trusts.
Planned Size of Sample (if applicable)	The target sample size for the randomised controlled feasibility trial is 72, with 36 participants allocated to each group.

	For the full trial, a sample of 740 participants (370 per group) would provide 80% power, with alpha=0.05 in two-tailed analysis.
Follow up duration (if applicable)	Phase I - 1-month follow-up. Phase II - 6-month follow-up.
Planned Study Period	Randomized controlled feasibility trial (Phase I; months 1-12), fully powered RCT (Phase II; months 13-48)
Research Question/Aim(s)	The main aim is to assess the effectiveness and costeffectiveness of providing an e-cigarette starter kit to people with mental Illness (PWMI) treated in the community to aid smoking cessation and harm reduction, as an adjunct to 'usual care'. The objectives of the proposed research are: 1. To test the feasibility and acceptability of the intervention and research processes in a randomized controlled feasibility trial (Phase I). 2. Based on findings from objective 1 and following potential refinement of intervention content and delivery, to assess the clinical and cost-effectiveness of the intervention for smoking cessation and harm reduction (Phase II).

FUNDING AND SUPPORT

FUNDER(S)	FINANCIAL AND NON FINANCIALSUPPORT GIVEN
Yorkshire Cancer Research	Financial Support
NIHR Clinical Research Network (CRN)	Non-financial – Study support service

ROLE OF STUDY SPONSOR AND FUNDER

The Sponsor

The sponsor of the trial is the University of York. The University of York holds insurance against claims from participants arising for negligent design and trial management for injury caused by their participation in this clinical trial (see section 7 on indemnity for more information).

The funder

Financial support for the trial has been provided from Yorkshire Cancer Research. Yorkshire Cancer Research have had no influence on the study design and will have no influence on the data collection and analysis of the feasibility trial or the main trial. NIHR Clinical Research Network (CRN) will provide non-financial support for the planning and set-up of the trial. CRN funded researchers will assist with the early stages of the trial.

NIHR CRN have had no influence on the study design and will have no influence on the data collection and analysis of the feasibility trial or the main trial.

ROLES AND RESPONSIBILITIES OF STUDY MANAGEMENT COMMITEES/GROUPS & INDIVIDUALS

Trial Steering Committee

Trial Steering committee membership to be confirmed - Within the first two months of the project start, we will appoint independent members to the TSC and DMC with oversight over both the feasibility and full RCT. The TSC will include a chair, clinicians, patient representatives, behavioural scientists, health psychologists, statisticians and health economists. The DMEC will comprise a medical doctor as chair and include experts in the field of tobacco control with experience of running large RCTs.

Patient & Public Involvement Group

The project will be supported by service users with lived experience of mental illness and smoking in the following ways: Brothers [name], a service user with severe mental illness and his carer (both ex-smokers), who are named co-applicants and centrally involved in its design from an early stage. In addition, we will convene a project-specific PPI group, recruiting patients and carers with interest in research from the participating Trusts' service user groups, utilising close contacts we have established in the context of previous research (including the recent SCIMITAR trial, led by [name], also a co-applicant). We estimate that our PPI group, which will be facilitated with support from [name], will have approximately six members from Yorkshire. Further PPI involvement will be facilitated and supported by our collaborators: Action on Smoking and Health (ASH) and a mental health charity (Equally Well).

The project relies on PPI involvement at all stages. PPI representatives from our core project team ([name]), our project-specific PPI group and charity collaborators (Equally Well at The Centre for Mental Health) will be consulted approximately every four months (more frequently if required) and involved in coproduction activities as research progresses. Complexities in this area, which include the heavy tobacco addiction experienced by many mental health service users, call for an approach that supports maximal service user orientation for the development of a relevant, acceptable and successful intervention. PPI representatives will be involved in the planning of the research, the development of service user-oriented intervention and research materials (e.g. leaflet), aspects of research conduct (e.g. development of topic guides for qualitative interviews in the pilot trial), networking with existing PPI groups nationally, and dissemination activities with a focus on informing national policy in this area.

STUDY FLOW CHART

Patient mental health records will be screened by research fellows prior to visits to CMHT or GP sites for CPA review/physical health screen. On appointment day, MHR or trained CPN will check eligibility and consent participants at community clinic/GP.

Inclusion criteria

[figure not shown]
 Participants who are current smokers, interested in cutting down or quitting; 2. No mental health inpatient stay in last 3 months; 3. Age ≥ 18 years; 4. Proficient in English or Urdu; 5. Capacity to provide consent

Exclusion criteria

 Current use of e-cigarettes;
 Participation in other smoking cessation trial within last 6 months;
 Pregnant or breastfeeding;
 No treatment for comorbid drug or alcohol problems in last 6 months;
 Alzheimer's disease or dementia diagnosis

Consented eligible participants

Baseline assessment (on site): sociodemographic/smoking behaviour characteristics, health behaviours, primary mental health diagnosis (if available), mental health history

^{*}From enrolment or target quit date (whichever is later; participants are given a week's grace period to set their quit date), carried out at community/GP dinks or at participant home; CMHT – Community Mental Health Team; GP – General Practitioner; CPA – Care Programme Approach; MHR – Mental Health Researcher; CPN – Community Psychiatry Nurse

ABREVIATIONS

Abbreviation Expansion

AE Adverse Event

BCT Behaviour Change Technique

BDCT Bradford District Care Trust

CMHT Community Mental Health Team

CPA Care Programme Approach

CPN Community Psychiatric Nurses

CRF Case Report Form

CSO Clinical Studies Officer

CTU Clinical Trials Unit

e-cigarette Electronic cigarette

ICER Incremental Cost Effectiveness Ratio

MHR Mental Health Researcher

NRT Nicotine Replacement Therapy

PPI Patient and Public Involvement

PWMI People With Mental Illness

QALYs Quality-Adjusted Life Years

RCT Randomised Controlled Trial

SAE Serious Adverse Event

SMI Severe Mental Illness

SSS Stop Smoking Services

SUTS Strength of Urges To Smoke

TEWV Tees, Esk and Wear Valleys NHS Foundation Trust

VBA Very Brief Advice

YCR York Cancer Research

1. BACKGROUND

Tobacco smoking remains the leading preventable cause of death and disease in England and is responsible for around 78,000 deaths annually [1], posing a financial burden of almost £3 billion to the NHS [2]. Despite smoking prevalence in the UK general population declining steadily over five decades, now standing at ~15% [3], no change has been observed among people with mental illness [4, 5]. With an average smoking prevalence of 40%, people with mental illness (PWMI) are more than twice as likely to be smokers as the general population [5], although smoking rates in this population can reach figures of up to 70% in subgroups such as hospitalised patients with severe mental illness (SMI)[5, 6]. Combined with high levels of nicotine dependence [7] which result in generally high cigarette consumption, this leads to substantially increased risks of smoking-related morbidity and premature mortality in PWMI [5], where up to 20 life years are lost largely to diseases related to smoking such as lung cancer, the biggest contributor to health inequalities [8].

Although PWMI are similarly motivated [9] and able [10] to quit smoking to those without mental illness, standard stop smoking services (SSS) are not commonly accessed by this population [11, 12], and are decreasingly resourced to support the need of smokers with SMI for tailored support [13-15]. Strong evidence that quitting smoking improves rather than exacerbates symptoms of mental illness [16], and may be causally linked to the development of mental illness [17] only emerged in recent years. Smoking until very recently remained deeply embedded in the culture of UK mental health settings [18], where it was commonly accepted as a coping mechanism for patients [5, 19, 20]. The 2013 joint Royal College of Physicians/Royal College of Psychiatrists report [5] and NICE guidance (PH48) [21] draw attention to the need to address this 'smoking culture'. The NICE guidance recommends that all mental health settings be entirely smoke free without exemption, with no facilitated smoking breaks, and evidence-based tobacco dependence treatment for smoking cessation, harm reduction and support for temporary abstinence available to all patients who smoke [21]. In line with goals of the Tobacco Control Plan for England and the NHS Long Term Plan mental health Trusts across the country are currently in the process of implementing the guidance, with evaluations underway [22, 23].

For many PWMI, contact with health professionals presents a 'teachable moment' [24] with opportunities to address smoking [25]. Research shows that opportunities to support smoking-related behaviour change could be better used in both inpatient [26] and community mental health settings [27]. The importance of developing smoking cessation interventions that are more effective than existing standard treatments for PMWI has been highlighted in various policy documents [21, 28, 29].

One of the largest smoking-related trials conducted among community patients with Severe Mental Illness (SMI), demonstrated that patients with SMI can successfully quit if intervention content is tailored to their needs [30]. SCIMITAR included existing evidence-based pharmacological and behavioural support but did not include any supported use of e-cigarettes (as these emerged only after the project had been designed). The smoking cessation-related support that was delivered by mental health practitioners more than

doubled quit rates at 6 months. In the context of NICE guidance PH48, mental health Trusts are now moving towards the kind of smoking cessation-related support provision that was tested in SCIMITAR, with results of this trial substantially influencing clinical practice. However, the design of the SCIMITAR study did not fully embrace the potential benefits of e-cigarettes in PWMI, described below.

E-cigarettes are popular; in England use by smokers and recent ex-smokers currently stands at around 20% and around 30% used e-cigarettes in quit attempts in 2021, compared with 3% of smokers accessing SSS [31]. E-cigarette use is increasingly being recorded by SSS [32], and appeal in particular to PWMI who are more likely to have tried e-cigarettes and be current users than smokers in the general population [33]. There are several reasons for this. Firstly, e-cigarettes are relatively cheap compared with both cigarettes and other cessation treatment [34]. Second, they offer a simple stand-alone treatment that is intuitive to use. Third, since e-cigarettes simulate the sensory input from cigarettes and allow users to control the dose (unlike most NRT), they may appeal to more dependent smokers who have hitherto struggled to quit, with the potential to enhance existing cessation treatments and replace combustible tobacco products [35]. Thus e-cigarettes may be one solution to reduce smoking and encourage cessation in mental health care settings by functioning as a safer alternative to cigarettes [36].

In the general population, more and more evidence is accumulating to show that ecigarettes are at least as effective a smoking cessation aid as NRT, both from randomised controlled trials (RCTs) [37-40] and real-world studies [41, 42]. In addition, there are small observational studies, which support their use for PWMI. Work carried out in Italy [43], the US [44] and Australia [45] found that e-cigarettes are effective for smoking cessation and reduction among smokers with SMI. More recently, a UK-based pilot study reported a significant reduction in average number of cigarettes smoked per day (≥ 50%) between baseline and 6-week follow-up, supporting the notion of e-cigarettes as a potentially successful harm reduction intervention for smokers with psychotic disorders [46]. These studies did not report any adverse effects for mental health, underlining the utility of ecigarettes as a tobacco harm reduction product for smokers with SMI. However, while these preliminary results are encouraging, to date no adequately powered RCT has assessed the effectiveness of e-cigarettes as a long-term (≥ 6 months) harm reduction and smoking cessation tool in everyday practice. This project therefore aims to assess the clinical and cost-effectiveness of the offer of an e-cigarette starter kit as an adjunct to usual care, compared with usual care alone, in a pragmatic RCT of PWMI treated in the community.

2. AIM AND OBJECTIVES

Our main aim is to assess the effectiveness and cost-effectiveness of providing an ecigarette starter kit to PWMI treated in the community to aid smoking cessation and harm reduction, as an adjunct to 'usual care' incorporating both a randomised controlled feasibility trial (Phase I; months 1-12) and a fully powered RCT (Phase II; months 13-48). This includes an embedded stop point after Phase I. The objectives of the research are:

- 1. To test the feasibility and acceptability of the intervention and research processes in a randomised controlled feasibility trial (Phase I).
- 2. Based on findings from objective 1 and following potential refinement of intervention content and delivery, to assess the clinical and cost-effectiveness of the intervention for smoking cessation and harm reduction (Phase II).

3. PHASE I – RANDOMISED CONTROLLED FEASIBILITY TRIAL (MONTHS 1-12)

3.1. Aim

We aim to conduct a randomised controlled feasibility trial of an e-cigarette starter kit (4-week supply and leaflet) as an adjunct to usual care for smokers with mental illness treated in the community.

3.2 Study objectives

- 3.2.1 Primary research objective: to assess the feasibility and acceptability of the ecigarette-based intervention and associated research processes in our study population, establishing central parameters for the design of a definitive RCT (Phase II), including recruitment and retention rates.
- 3.2.2 Secondary research objectives: (1) to determine whether progression to a full trial is reasonable, based on the confidence interval approach [47] (see also 1.9); (2) to establish e-cigarette adherence rates and potential level of contamination between study arms to inform planning for a full trial; (3) to assess fidelity of intervention delivery; (4) to establish the feasibility of data collection and training procedures and pilot the gathering of cost data to inform methods for health economic analysis in Phase II; (5) to explore barriers and facilitators to participation; (6) if indicated, to refine the intervention and study protocol in readiness for a full RCT.

3.3 Study design

Phase I will consist of a randomised controlled feasibility trial with an embedded process evaluation, comparing the intervention (e-cigarette starter kit as an adjunct to usual care) and control groups (usual care) at 1-month follow-up.

3.4 Treatment groups

3.4.1 Intervention group - E-cigarette starter kit as adjunct to usual care

The intervention group will be offered an e-cigarette starter kit, compliant with EU regulation, and an information leaflet about e-cigarettes, in addition to usual care. Usual care differs between (and sometimes within) Trusts but is guided by NICE guidance PH48 [48], with a minimum standard of evidence-based very brief advice (VBA) to stop smoking, comprising the three As: Ask and record smoking status; Advice on the best way of quitting and Act on patient response to build confidence, and referral to in-house or external specialist stop smoking services.

The e-cigarette starter kit containing an e-cigarette a four-week supply of e-liquid and an information leaflet will be provided to participants in the post for those on the online pathway (pathway 1 – will be sent a letter with instructions not to start using this until after the intervention) and in person at their appointment for those on pathway 2 (see 3.6.3). A third-generation e-cigarette with a refillable tank from a tobacco industry independent manufacturer will be offered, for example the Aspire PockeX, which was used in a recent trial that provided evidence of a superior effect of e-cigarettes over standard nicotine replacement therapy [49]. There is good evidence that these products are more effective in delivering nicotine than others [50]. The choice of e-liquid will be based on the most popular flavour and concentration combinations in the UK [51].

Participants of the feasibility trial in Phase 1 will be provided with a selection of different flavours (tobacco, fruit, and menthol) as well as different concentrations (Concentrations offered will vary between 6 mg/ml to 20 mg/ml) to allow them to experiment and select their preferred choice of flavour/nicotine concentration combination. This will also help us establish preferences in this patient population for the full trial in Phase II to minimise negative responses to using the e-liquid. In addition, advice on the use of e-liquid and encouragement to contact the research team by email or telephone if the liquid is not accepted well will be provided for the full trial in Phase II where participants can choose only one of several flavour/nicotine concentration combinations. Participants who perceive the e-liquid to be aversive will be posted replacement e-liquid.

At a scheduled appointment with a clinician, a brief consultation will be conducted with participants to provide necessary instructions for use of the kit. This appointment can be an online if this is usual practice for those on the online pathway. All participants will be encouraged to consider quitting and to set a target quit date within a week. As set quit dates are likely to vary widely and may change over time, all participants will have a two week 'grace period' from enrolment to decide whether they chose to set a target quit date or not. Participants will be asked to start using the e-cigarette when they quit and to seek out local vape shops to obtain further e-liquid, suited to their individual needs and flavour preference. Participants who do not wish to set a target quit date will be encouraged to use the e-cigarette to reduce cigarette consumption as soon as possible.

3.4.2 Control group - Usual care

The control group will receive care as usual, as outlined above. As is common practice in pragmatic 'real-life' trials that involve variations of 'usual care' across organisations and localities, we will record the characteristics and details of usual care provided at each site to take these into account in the analyses and will codify treatment content in both groups using a well-established behaviour change taxonomy commonly used in tobacco research [52].

3.5 Randomisation and allocation concealment

The intervention allocation will be determined by block computer-randomisation to ensure that each trial site has an equal proportion of intervention and control group participants. Those on the online pathway (pathway 1; see 3.6.3) will be informed electronically via email and those on the paper-based pathway (pathway 2; see 3.6.3) will

open a sealed envelope at their appointment. Randomisation will occur after consent to take part in the study has been obtained. Due to the nature of the intervention, it will not be possible to blind participants or all researchers to treatment allocation. The lead applicants, co-applicants, and statisticians, however, will be blinded.

3.6 Participants and procedures

3.6.1 Participants

Participants will include adults (> 18 years) receiving treatment for a mental illness under the care of secondary care psychiatric community teams or community mental health teams (CMHTs) at three Northern Mental Health Trusts (see 3.7). Smokers (who smoke regularly and have smoked combustible cigarettes in the past 7 days) with any mental health condition will be eligible to participate. However, to reduce the possibility of hospital admission for acute events (and thus the risk of drop-out), patients must not have had an inpatient admission in the last 3 months according to their health care record. Participants must be willing to address their smoking behaviour, either by attempting to quit or by reducing their consumption and have capacity to provide consent. Smokers who are currently using e-cigarettes regularly (at least weekly), are participating in other smoking cessation trials, are being treated for comorbid drug or alcohol problems, have a diagnosis of Alzheimer's disease or dementia, or are pregnant or breastfeeding will be excluded. Reasons for exclusion and, for eligible patients, reasons for non-participation will be documented where possible/provided.

3.6.2. Recruitment

Each Trust will be allocated a part-time dedicated MHR to support project delivery in the respective localities. Patients with an appointment planned in the coming weeks will be invited to part by letter, which will be sent from the patient's mental health team, or GP surgery for primary care patients. A follow-up call or text will be sent after 7 days.

3.6.3 Procedure

Participants from Mental Health Trusts (Secondary Care) will be identified via health records prior to attendance at an up-and-coming appointment. A list of potential participants will either be checked for smoking status by clinical studies officers (CSOs) or a care coordinator/other appointed person at a GP surgery for primary care. Participants who smoke will then be contacted by letter containing the participant information sheet in advance of their appointment to ascertain interest in the study and may also receive a follow-up call to check they have received the letter. Those who are interested will be asked to respond to indicate this either verbally over the telephone, by advice slip in the post or using an online link. They will then receive a call from the research team to check eligibility using the checklist and answer questions which participants have relating to the study. If interest in participation is confirmed informed consent will be sent electronically (pathway 1). There will also be a paper-based option available for those who do not wish to use the electronic option. In this case, participant information and consent forms will be given in person at a scheduled appointment.

Eligible, consented participants will be asked to complete a brief baseline questionnaire, which will be administered via GDPR-compliant online survey tool REDcap (or in person at the same scheduled appointment as consent, which will require the participant to attend their appointment 30 minutes early to meet with the CSO) assessing sociodemographic and smoking behaviour characteristics, with mental health diagnosis and history being obtained from health care records. For those following the online pathway, once a participant has completed and returned the baseline assessment materials, a link will be sent to the participant to inform them of which group they have been randomised to. For those on the paper-based pathway this will be done in person via a sealed envelope (randomisation will have been generated prior to this by computerised block randomisation at the UCL Clinical Trials Unit see 3.4). At this stage, interaction with participants allocated to the control group will stop to allow them to attend their appointment and receive care as usual. Participants allocated to the intervention group will also attend their appointment and receive care as usual but in addition will receive the e-cigarette starter kit, a leaflet and brief explanation (see 3.5.1).

Follow-up of participants at 1 month in phase 1, and at 1 and 6 months in phase 2, will be undertaken by dedicated mental health researchers. Follow-up surveys will be completed via telephone with an option to receive this by post if preferred. In-person follow up at CMHT sites or participants' homes will be required to biochemically validate self-reported abstinence only through carbon monoxide readings (likely to affect approximately 12 participants in phase 1, and 94 participants in phase 2 as per expected abstinence in control and intervention arms in both the feasibility and full trial; see subsections 3.9 and 4.6 of the submitted application). Figure 1 shows a flow diagram of the participant journey through the study. For COVID-19 risk management, social distancing and hygiene measures will be strictly observed and the study team and participants briefed in advance of the follow up visit. Individual mouth pieces for the monitors will be discarded immediately after use and the monitor core piece disinfected. Staff and participants will be provided with PPE – surgical face masks and plastic gloves.

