We do not anticipate involving a dedicated CTU in this research project, given extensive experience of the administration and day-to-day running of large-scale smoking cessation RCTs at our Department at UCL without an CTU (e.g. [102, 103]) and the involvement of an experienced statistician (EB) in this project. We will, however, avail of ad-hoc CTU services provided at UCL for some aspects of the trial, including randomisation, case report form (CRF) checks and database development.

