6. DATA STORAGE AND DATA PROTECTION

Data will be stored in accordance with the Data Protection Act 1998. All data will be collected electronically and stored on a password protected server at UCL using REDCap (a secure web-based data storage system) within their Data Safe Haven system. Participants' identification numbers will be used to uniquely identify patients on the online electronic case report form. All other essential documents, including source documents, will be retained for a minimum period of 10 years after study completion.

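### Paper-pathway allocation by sealed envelope at the appointment, with no stated safeguard and no rule for sharing a site's sequence with the online pathway, leaves concealment weaker than it need be

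*Protocol*

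**What the plan says.** Protocol section 3.5 allocates by "block computer-randomisation to ensure that each trial site has an equal proportion of intervention and control group participants". Block size, and whether it varies, are not given. Participants on the online pathway are told by email. Those on the paper pathway "open a sealed envelope at their appointment".

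Section 3.6.3 repeats the two routes. Online, once the baseline form is returned, "a link will be sent to the participant to inform them of which group they have been randomised to". On paper: "For those on the paper-based pathway this will be done in person via a sealed envelope". It adds that "randomisation will have been generated prior to this by computerised block randomisation at the UCL Clinical Trials Unit". Paper-pathway consent forms are handed over at the scheduled appointment and the baseline questionnaire is completed there too, so consent, baseline and envelope fall within one visit.

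Section 3.5 puts randomisation after consent. It says that participants and some researchers cannot be blinded, and names the lead applicants, co-applicants and statisticians as blinded. The study flow chart has the mental health researcher or a trained community nurse check eligibility and take consent on the day. Section 3.8.2.1 describes the same roles as delivering the intervention.

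The paragraph closing section 4.7.2 says that the trial will "avail of ad-hoc CTU services provided at UCL for some aspects of the trial, including randomisation". Section 4.2 intends a similar approach to randomisation in the full trial, optimised on the Phase I findings.

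**The concern.** In an open trial, concealment depends on nobody who decides on entry being able to learn the next allocation. Envelopes prepared before the visit put that allocation within physical reach of the clinic, and the protocol does not say how it is protected there. There is room for selection. Entry turns on willingness to address smoking, only about 15% of eligible patients are expected to consent (3.8.2.1, 3.9), and motivation to quit plausibly affects abstinence. If recruitment leaned even slightly towards more motivated smokers when the kit was expected next, the arms would differ at baseline in a way that favours the intervention.

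Two decisions are exposed. In Phase I, the abstinence comparison feeds the stop/go criteria in 3.13. In Phase II, the 740-participant primary comparison would inherit the method.

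**Working it through.** The protocol gives no figure for concealment, so there is none to reproduce. The check compares its statements and adds two small calculations.

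**1. What protects the paper-pathway allocation?**

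| Element | Stated? | Where |
|---|---|---|
| Sequence generated by the CTU | Yes | 3.6.3 |
| Allocation after consent | Yes | 3.5 |
| Participant opens the envelope | Yes | 3.5 |
| Envelopes opaque, sequentially numbered, logged | No | – |
| Who holds the envelopes | No | – |
| Block size varied or withheld from sites | No | – |
| How the two pathways share a site's sequence | No | – |

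**2. Can one site list serve both routes?** An envelope prepared in advance is tied to a list position. Suppose an online participant is randomised after the envelope is prepared but before it is opened. Either the online participant takes the next position and the envelope is then used out of order, or positions are reserved for envelopes, which amounts to a second list for that site. Either could be managed, but the protocol describes neither.

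**3. How predictable are site-level blocks?** Block size is an assumption here. Take a fixed block of 2m with m per arm, a recruiter who knows the size, and sight of every earlier allocation.

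- Share of allocations that are certain: 1/(m+1).
- Share guessed correctly by always naming the under-represented arm: [m + (4^m / C(2m,m) − 1)/2] / (2m).

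| Block size | Certain | Correct guess |
|---|---|---|
| 2 | 1/2 = 50% | [1 + (4/2 − 1)/2]/2 = 1.5/2 = 75% |
| 4 | 1/3 = 33% | [2 + (16/6 − 1)/2]/4 = 2.833/4 = 71% |
| 6 | 1/4 = 25% | [3 + (64/20 − 1)/2]/6 = 4.1/6 = 68% |

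These agree with full enumeration of the blocks. They come from blocking, not from envelopes. For a central list with blocks of 2, 4 and 6 chosen at random with equal chance (also an assumption), the same guessing rule is right (1.5 + 2.833 + 4.1)/(2 + 4 + 6) = 8.433/12 = 70% of the time. Withholding the sizes mainly reduces the share known for certain. Central release removes something different: the chance to open, hold back or reorder an envelope.

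**4. Would two lists per site spoil site balance?** A list in blocks of b is never more than b/2 out of balance, so two lists together are never more than b out. With b = 4 assumed, the greatest arm difference at a site is 2 for one list and 4 for two. Balance loosens slightly.

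**5. Size of bias.** This would need the paper-pathway share, how often the next allocation is foreknown, and how far participants selected on that knowledge differ in their chance of quitting. The protocol gives none of these, so no figure can be computed.

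**The case against.** The strongest reply is that the protocol already provides the essentials (a CTU-generated sequence, sealed envelopes, allocation after consent), and that envelope specification and block size belong in a randomisation procedure, where block size is often deliberately kept from sites. That stands in part: the absence of such details alone would be a weak complaint. But the envelope is a stated choice of method, and a better one can be had through a service the protocol names.

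Four stronger readings should be resisted:

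- A reader might infer that recruiting staff hold the envelopes. Custody is not stated. Section 3.6.3 has the research team check eligibility by telephone and the paper-pathway participant meet a clinical studies officer, whereas the flow chart names the researcher or nurse. Overlap of roles is possible, not established.
- A reader might infer that two routes undo the site balance. Step 4 shows that they would not.
- A reader might infer that no analysis could repair the bias. Motivation to quit and dependence are measured at baseline (3.8.1.2), and section 4.7.1 adjusts for known predictors of cessation. Selection on measured motivation is partly addressed; unmeasured selection is not.
- A reader might take the online route as evidence that on-demand randomisation is already running. Sections 3.5 and 3.6.3 describe electronic notification only. What is available is the CTU randomisation service.

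It is also fair that the envelope wording sits in Phase I, whose estimate is not used directly as the effect (3.9), and that section 4.2 leaves room to change. Carry-over is likely rather than fixed, which is a reason to settle it now.

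**Conclusion.** The point holds as a cheap improvement to a stated method. Concealment on the paper pathway is weakened, not absent, by the combination of pre-prepared envelopes, site-level blocks, an open trial, possible overlap of recruiting and delivery roles, and no stated safeguard or rule for combining the pathways. That blocks run within site is the natural reading of section 3.5, and that recruiters may see allocations is an inference from the flow chart, 3.5 and 3.8.2.1.

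The bias cannot be sized. The 68% to 75% guess rates only illustrate fixed blocks of known size with all past allocations seen. They are neither the effect of the envelopes nor the gain from removing them. No sample size or power figure changes.

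**What to change.** In sections 3.5 and 3.6.3, and before Phase II adopts the same approach, replace the envelopes with central release through the UCL CTU randomisation service already named:

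- one list per site, used for both pathways in order of randomisation;
- allocation released online or by telephone only after consent and baseline are recorded;
- randomly varying block sizes, withheld from sites.

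Both parts are needed: central release keeps the next allocation out of the clinic, and varied, undisclosed block sizes reduce what can be known for certain from past allocations.

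If envelopes stay as a backup, state that they are opaque, sequentially numbered and logged, and held by someone who does not recruit. State also how their positions relate to the online allocations at the same site.

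The cost is a small set-up task and the need for an internet or telephone connection at the appointment.
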